1. SPECIFIC AIMS

Moderate or severe aortic stenosis (AS) affects 2.8% of people aged \geq 75 years and is one of the most common valvular disorders worldwide⁽¹⁾. Without intervention, severe AS carries an extremely poor prognosis with a 1 and 5 year survival of ~60% and ~30%, respectively^(2,3). Surgical and transcatheter aortic valve replacement (AVR) are to-date the only interventions that have been shown to improve morbidity and mortality in this population^(4,5). However, there is heterogeneity in clinical course after AVR; even after a successful procedure, some patients show minimal symptomatic or hemodynamic improvement⁽⁶⁾.

Symptoms in aortic stenosis result from an inability of the left ventricle (LV) to overcome the systolic load caused by a fixed outflow obstruction. After correction of the stenotic valve, residual LV afterload results primarily from arterial load and is associated with poor outcomes. Indeed, higher pulsatile arterial load after AVR is significantly associated with mortality⁽⁷⁾. An important component of pulsatile load is the magnitude of wave reflections in the arterial tree^(8,9). Wave reflections arise in peripheral arterial sites and travel back to the heart, arriving while the LV is still ejecting blood, increasing the late systolic workload of the LV. Wave reflections are highly sensitive to nitric oxide (NO).

The increased LV afterload during systole results in myocyte hypertrophy and increased wall thickness that is accompanied by a diffuse interstitial fibrosis in the myocardium⁽¹⁰⁾. In fact, the amount of myocardial fibrosis, as determined by either histology or cardiac MRI, is an independent predictor of LV function improvement and late all-cause mortality after aortic valve replacement ⁽⁶⁾. However, myocardial fibrosis does not appear to regress significantly after aortic valve replacement ⁽⁶⁾. However, myocardial fibrosis does not appear to regress significantly after aortic valve replacement ^(11,12). This suggests that arterial factors play a role in the pathogenesis and maintenance of fibrosis even after AVR. This additionally indicates that persistent myocardial fibrosis may contribute to poor quality of life after AVR. Thus, reducing fibrosis, by reducing wave reflections and arterial load, may be an effective strategy towards improving quality of life and exercise capacity in patients after aortic valve replacement for severe aortic stenosis.

Prior data demonstrates that a single oral dose of inorganic nitrate reduces late systolic load in other populations. Dietary nitrate increases plasma nitrite, an endothelium-independent source of the potent vasodilator nitric oxide (NO). Thus, augmentation of the nitrate-nitrite-NO pathway has the potential for chronic "disease-modifying" benefits in aortic stenosis. Therefore, nitrate supplementation represents a logical intervention to improve exercise capacity and quality of life in aortic stenosis.

The current trial is designed to assess the safety and efficacy of sustained oral administration of inorganic nitrate in patients with severe aortic stenosis and to assess the mechanisms by which inorganic nitrate enhances oxygen uptake and exercise capacity in this population. This is a randomized double-blind crossover clinical trial, in which 22 subjects who underwent surgical or transcatheter AVR for severe AS three or more months prior to enrollment will receive the following 2 interventions, in randomized order: (1) Potassium nitrate (KNO₃), at a dose of 12-18 mmol/d by mouth for 4 ± 1 weeks, or; (2) Potassium chloride (KCI), at a dose of 12-18 mmol/d by mouth for 4 ± 1 weeks. A 1-week ± 3 day washout period will be introduced between the 2 interventions. The purpose of the trial is to test the safety of KNO₃ and its efficacy on a number of clinical and physiologic endpoints in subjects who underwent AVR for severe AS.

Our specific aims are:

Specific Aim 1: To assess whether KNO_3 therapy improves endpoints with direct clinical relevance: aerobic capacity and quality of life (QOL)

Hypothesis 1a: KNO_3 will improve exercise capacity, quantified as: (1) Total work performed during a maximal-effort exercise test; (2) Peak oxygen consumption (VO₂) during a symptom-limited maximal effort exercise test. These will be the co-primary endpoints of the trial.

Hypothesis 1b: KNO_3 will improve QOL, assessed using the Kansas City Cardiomyopathy Questionnaire.

Specific Aim 2: To dissect the effects of KNO₃ on specific physiologic adaptations to exercise

Hypothesis 2a: KNO_3 improves the systemic vasodilator response to exercise, measured as the change in systemic vascular resistance during a symptom-limited maximal effort exercise test.

Hypotheses 2b: Since nitrates may exert venodilating effects and/or myocardial effects, we will test the hypotheses that KNO₃ impacts LV diastolic filling parameters (measured with echocardiography at rest and after peak exercise) and improves myocardial strain (assessed with speckle-tracking echocardiography).

Specific Aim 3: To assess whether KNO₃ reduces late systolic LV load from wave reflections (assessed via comprehensive aortic pressure-flow relations, using arterial tonometry and Doppler echocardiography).

This trial has the potential to establish a novel, inexpensive, and readily implementable therapeutic paradigm for post-AVR patients and to characterize specific mechanisms involved, enhancing our understanding of this disease.

2. TRIAL SUMMARY TABLE (OBJECTIVES AND ENDPOINTS)

Trial Title / Acronym	Targeting Pu lsatile Load to Increa s e E xercise Capacity and Quality of Life After Aortic Valve Repair for Severe A ortic S tenosis (PULSE AS)					
Phase	Phase IIb Randomized Clinical Trial (RCT)					
Number of Subjects	22					
Patient Population	Ages 50-90; 3 or more months after AVR for severe AS					
Study Site	University of Pennsylvania					
Study Design	Randomized, double-blinded crossover study					
Randomized Intervention	Potassium Nitrate (KNO ₃) capsules, at a dose of 6 mEq (1 capsule) three times daily for 4 ± 1 weeks, versus, potassium chloride (KCI) capsules administered at a dose of 6 mEq (1 capsule) three times daily for 4 ± 1 weeks					
Primary Aim	To assess whether KNO_3 therapy improves exercise capacity, quantifier as: (1) Total work performed during a maximal-effort exercise test; and (2) Peak oxygen consumption (VO ₂) during a symptom-limited maximal effort exercise test. These will be the co-primary endpoints of the trial.					
Secondary Aims	 To assess whether KNO_{3:} improves quality of life improves the systemic vasodilator response to exercise improves LV diastolic function and myocardial systolic strain reduces late systolic LV load from wave reflections 					
Exploratory Aims	To assess whether KNO ₃ improves:					
	 Ventilatory threshold, VO₂ kinetics Natriuretic peptide levels Physical activity 					
	To assess the relationship between nitrate and nitrite levels achieved and the therapeutic response achieved in each subject (e.g., improvement in endpoints in response to KNO ₃ vs control). To assess the effect on RNA expression.					
Primary Endpoints	Peak oxygen uptake (VO₂) during a symptom-limited maximal effort exercise test after 4 ± 1 weeks of KNO ₃ vs KCI					
	Quality of life score , assessed using the Kansas City Cardiomyopathy Questionnaire					
Secondary Endpoints	Measures of LV diastolic function (E/e', left atrial volume index),and peak global systolic myocardial longitudinal and circumferential strain					
	Augmentation index, late systolic wall stress and aortic input impedance					

3. BACKGROUND AND SIGNIFICANCE

Calcific aortic stenosis (AS) occurs in 3-5% of people in the United States aged \geq 75 years⁽¹³⁾. Without intervention, severe AS carries an extremely poor prognosis with a 1 and 5 year survival of ~60% and ~30%, respectively^(2,3). Surgical and transcatheter aortic valve replacement (AVR) are currently the only interventions that have been shown to improve morbidity and mortality in this population^(4,5). Over the last decade, TAVR has been shown to result in a dramatic improvement of survival and quality of life for many patients who were deemed to be inoperable candidates for SAVR^(4,5). However, there is heterogeneity in clinical course after AVR; even after a successful procedure, some patients show minimal symptomatic or hemodynamic improvement⁽⁶⁾. Among the extreme risk cohort of patients in the CoreValve US Pivotal trial, 39% of patients had a poor outcome 6 months after TAVR with 22% dying, 6% having poor quality of life by KCCQ and 1.4% with with a decline in their quality of life after the procedure⁽¹⁴⁾. This was redemonstrated in reports from the PARTNER trial, in which 35% of patients had a poor outcome at 6 months post-procedure, with 19% subsequently dying and 16% with poor quality of life⁽¹⁵⁾. This suggests an unmet need to identify and intervene upon physiologic abnormalities in patients who do not benefit from TAVR.

There are a number of factors that determine a patient's functional health status after AVR. Given the relative advanced age of patients who undergo TAVR, it should come as no surprise that presence of co-morbidities and overall frailty, in addition to age and gender, are critical. An analysis of patients from the PARTNER trial identified a number of significant pre-procedure risk factors that were predictive of poor outcomes after TAVR. Poor functional capacity, measured by Six-Minute Walk Test (6MWT) and lower mean aortic valve radients were the most predictive; other predictors were renal dysfunction, oxygen-dependent lung disease, and poor baseline cognitive function⁽¹⁶⁾. There are also clear cardiac and systemic hemodynamic characteristics that are associated with poor outcomes after AVR. Low-gradient AS and tricuspid valve regurgitation were shown to be associated with all-cause 6 month post-procedure mortality; severe mitral regurgitation and moderate/severe postprocedural aortic regurgitation appear to be independent predictors of poor response to treatment⁽¹⁷⁾. Higher pulsatile arterial load after aortic valve repair is significantly associated with mortality⁽⁷⁾.

Symptoms in aortic stenosis result from an inability of the left ventricle to overcome the systolic load caused by a fixed outflow obstruction. Left ventricle (LV) afterload in patients with severe AS can be conceptualized as a series circuit with additive contributions by both the aortic valve and systemic arterial tree^(8,9,18). After correction of the stenotic valve, residual LV afterload results primarily from arterial load and is associated with poor outcomes. Indeed, higher pulsatile arterial load after AVR is significantly associated with mortality⁽⁷⁾. An important component of pulsatile load is the magnitude of wave reflections in the arterial tree^(8,9). Wave reflections arise in peripheral arterial sites and travel back to the heart, arriving while the LV is still ejecting blood, increasing the late systolic workload of the LV. Available evidence causally link late systolic load with LV remodeling, diastolic dysfunction, and HF risk. Wave reflections are highly sensitive to NO.

The increased LV afterload during systole results in myocyte hypertrophy and increased wall

thickness, which allows the ejection fraction to be maintained by decreasing LV wall stress⁽¹⁹⁾. This myocyte growth is accompanied by a diffuse interstitial fibrosis in the myocardium, as fibroblasts increase collagen synthesis in response to the elevated intraventricular pressures⁽¹⁰⁾. In fact, the amount of myocardial fibrosis, as determined by either histology or cardiac MRI, is an independent predictor of LV function improvement and late all-cause mortality after aortic valve replacement⁽⁶⁾. However, myocardial fibrosis does not appear to regress significantly after aortic valve replacement^(11,12). This suggests that nonvalvular factors may play a role in the pathogenesis and maintenance of fibrosis even after AVR.

Our trial will test a novel intervention (inorganic nitrate) to modify key physiologic abnormalities (arterial vasodilator reserve and late systolic LV load from arterial wave reflections), which have the potential for both immediate-term improvements in exercise tolerance and long-term "disease-modifying" effects. The trial is designed to address the safety and potential clinical benefit of this approach in severe aortic stenosis using endpoints with direct clinical relevance, and also to characterize the specific physiologic mechanisms involved. This will potentially identify a new therapeutic paradigm and a readily implementable therapeutic intervention.

4. STUDY DESIGN AND POPULATION

4.1. Overview of study design

In this phase IIb, double-blind, cross-over trial, we will assign 22 subjects who are post-AVR for severe AS to: (A) Potassium nitrate administered by mouth at a dose of 6 mEq three times daily for 4 ± 1 weeks, or (B) Potassium chloride (KCl) at identical doses. The order of the interventions (AB-BA design) will be randomized, with a 1-week \pm 3 day washout period separating each intervention. A crossover design will enable each subject to receive both treatments, reducing inter-individual variability and maximizing our power to detect effects of potassium nitrate vs. control (KCl). The active drug (KNO₃-) and control (KCl) will be prepared at the Investigational Drug Pharmacy at the University of Pennsylvania and dispensed by an investigational drug pharmacist, blinded to both the subjects and the investigators.

4.2 Study Sites

The site for this trial will be the Hospital of the University of Pennsylvania.

4.3. Study Population

Subjects will be identified from clinic visits at the University of Pennsylvania for post-TAVR follow up. We will enroll 22 subjects meeting the following criteria:

4.3.1. Inclusion Criteria

- 1. Adults aged 50-90 years of age
- 2. Diagnosis of severe aortic stenosis prior to aortic valve repair
- 3. Successful trancatheter aortic valve repair via transfemoral procedural approach or successful surgical aortic valve repair at least three months prior to enrollment

4. Stable medical therapy: no addition/removal/changes in antihypertensive medications, or beta-blockers in the preceding 30 days.

4.3.2. Exclusion Criteria

- Supine systolic blood pressure (SBP) < 100 mmHg OR supine diastolic blood pressure (DBP) <60 mmHg
- 2. Poorly controlled hypertension, as defined as SBP > 160 mmHg OR DBP > 100 mmHg
- 3. Pregnancy. Women of childbearing potential will undergo a pregnancy test during the screening visit
- 4. Atrial fibrillation within the prior 8 weeks before enrollment
- 5. Inability/unwillingness to exercise
- 6. Moderate or greater mitral regurgitation or aortic/perivalvular regurgitation, any degree of mitral stenosis, severe right-sided valvular disease, or presence of a mitral prosthetic valve.
- Moderate or severe patient prosthesis mismatch, as defined by Effective Orifice Area Index < 0.85 cm²/m²
- 8. Hypertrophic, infiltrative, or inflammatory cardiomyopathy
- 9. Pericardial disease
- 10. Current angina
- 11. Acute coronary syndrome or coronary intervention within the past 2 months
- 12. Primary pulmonary arteriopathy
- 13. Clinically significant lung disease as defined by: Chronic Obstructive pulmonary disease meeting Stage III or greater GOLD criteria, treatment with oral steroids within the past 6 months for an exacerbation of obstructive lung disease, or the use of daytime supplemental oxygen
- 14. Ischemia on stress testing without subsequent revascularization (during the screening visit)
- 15. Treatment with phosphodiesterase inhibitors that cannot be withheld
- 16. Treatment with organic nitrates
- 17. Significant liver disease impacting synthetic function or volume control (ALT/AST > 3x ULN, Albumin <3.0 g/dL)
- 18. eGFR < 30 mL/min/1.73 m²
- 19. G6PD deficiency. For males of African, Asian or Mediterranean decent, this will be evaluated prior to drug administration. A qualitative test positive for deficiency or a quantitative test with clinically significant G6PD deficiency (<60% of normal activity) will prompt exclusion from the trial (prior to drug administration).
- 20. History of methemoglobinemia or methemoglobin level >5% at baseline visit
- 21. Serum K>5.0 mEq/L
- 22. Severe right ventricular dysfunction.
- 23. Any medical condition that, in the opinion of the investigator, will interfere with the safe completion of the study.
- 4.3.3. Criteria that will prompt exclusion from the trial at the phase 1 visit
- 1. Acute coronary syndrome or coronary intervention for unstable coronary disease after enrollment
- 2. New onset ischemia on stress testing since the time of enrollment
- 3. New treatment with organic nitrates or phosphodiesterase inhibitors that cannot be withheld.

- 4. Serum K>5.5 mEq/L.
- 5. Any medical condition that, in the opinion of the investigator, will interfere with the safe completion of the study, or the validity of endpoint assessments. These ad-hoc discontinuations will be discussed with the PI of the trial and the medical director of the IND.

In the following situations, subjects who meet the criteria below will not be immediately discontinued, but will be scheduled for an ad hoc visit for reassessment of values prior to drug initiation in phase 2:

- 1. Supine systolic blood pressure < 90 mm Hg
- 2. Acute kidney injury with eGFR < 30 mL/min/1.73m2
- 3. Methemoglobinemia baseline methemoglobin level > 5%

If these criteria persist during the ad-hoc visit, the subject will be discontinued from the study.

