5.4. Washout period

Following the endpoint assessment, subjects will enter a 1-week \pm 3 day washout period during which they will not receive any study medications.

At 3 weeks into each interventional phase, the Actigraph device will be mailed to the subjects. The goal will be for the subjects to wear this devices on their wrist during the final week of each interventional phase to look for differences with each therapy. The device will be returned by the subject at the endpoint assessment.

5.5. Intervention Phase 2

Following the washout period, subjects will receive either active drug (KNO₃) or control (KCI) during phase 2 of the trial. Subjects will receive the intervention (KNO₃ or KCI) that was not administered to them in phase 1, such that each subject will receive both study interventions in this cross-over design. The ~1-week call and the ~4-week study visit will be repeated as above. We will provide subjects with a 14-day supply of study medication to account for potential delays in receipt of the 2nd batch of medication (i.e., after the 1-week call).

1-week call: Subjects will be called by telephone ~1 week later to assess if they are experiencingside-effects. Subjects will receive reinforcement of the dietary restrictions imposed during the study. Subjects will be asked about headaches and dizziness. If these symptoms are not present, or are not different than the subject's baseline, the drug dose will be up-titrated to 18 mmol daily (One 6-mmol capsule taken 3 times per day). The presence of orthostatic symptoms will prompt a visit to assess for orthostatic vital signs. The presence of symptomatic orthostatic hypotension (20 mmHg reduction in systolic blood pressure with associated symptoms such as dizziness) at the follow up visit will prompt exclusion of patients from the trial.

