11.2.1. Potential Risks of study intervention (potassium nitrate)

The main potential risks of nitrate administration are related to its potential effect on (1) blood pressure; and (2) methemoglobin levels.

Effects on blood pressure: Regarding the blood pressure reduction, as described above, many studies have demonstrated a reduction in blood pressure in both hypertensive and normal subjects following nitrate supplementation. This was summarized in a recent meta-analysis, demonstrating an approximate 4 mm Hg reduction in systolic blood pressure and 1 mm Hg reduction in diastolic blood pressure.⁽⁴³⁾ Importantly, in a study by our group of a single dose of inorganic nitrate in subjects with HFpEF, we did not observe any change in blood pressure following nitrate ingestion. Importantly, the lack of a blood pressure response to nitrate has been shown in both elderly⁽¹²⁵⁾ and diabetic individuals,⁽¹²⁶⁾ suggesting that there may be important differences in nitrate effect by subgroups. In our pharmacokinetics study, we found a mild (~12 mm Hg) asymptomatic reduction in blood pressure recorded at the time of our study visits during 2-week drug administration, which occurred in the absence of any hypotensive symptoms.⁽¹²⁷⁾ We did not find a reduction in ambulatory blood pressure. Therefore, although we do not anticipate major changes in BP or significant hypotension with this dose, we will implement exclusion criteria and safety blood pressure checks throughout the conduct of the study to ensure subject safety (see next section).

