11.3.2. Protection against risks associated with cardiopulmonary exercise tests

These tests will be performed by qualified personnel according to established American Heart Association Guidelines(142), under ECG monitoring. Personnel with adequate cardiopulmonary resuscitation training and resuscitation equipment (crash cart) will be available during these tests. Similarly, these tests will be performed in a hospital setting where a full code team can be deployed immediately should complications occur.

11.3.3. Protection against risks of potassium nitrate administration:

Subjects will be thoroughly advised regarding the potential risks of the study medication and precautions needed during its administration. We will exclude individuals who are taking sildenafil (Viagra®), tadalafil (Cialis®), or vardenafil (Levitra®) and we will instruct them not to take these medications while participating in the study, since it is likely that these medications may exaggerate the vasoactive effects of potassium nitrate. Similarly, the use of organic nitrate will be contraindicated during participation in this trial.

Supine and orthostatic blood pressure measurements: Supine vital signs will be measured at the screening visit. The subject will rest in a supine position for a minimum of 3 minutes prior to obtaining vital sign measurements. Subjects with a supine systolic blood pressure >110 will be enrolled in the study. The subject will then assume a standing position for 3-5 minutes. Vital signs (BP and pulse rate) will then be measured while the subject is standing. A reduction in systolic blood pressure >20 mmHg will be considered an exclusion criterion for the study. Blood pressure measurements will be repeated after 4 ± 1 weeks of randomized therapy. Measurements will also be prompted by reports of any report of orthostatic symptom by study subjects at any point during the trial. The presence of symptomatic orthostatic hypotension (20 mmHg reduction in systolic blood pressure with associated symptom such as dizziness) will prompt exclusion of patients from the trial.

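### The supine blood pressure limits for starting study drug disagree across sections 4.3.2, 4.3.3 and 11.3.3, and the loosest is the one nearest first KNO3 exposure for about half the subjects

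*Combined protocol and SAP*

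**What the plan says.** All references are to the combined protocol and SAP.

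- **Entry, section 4.3.2.** The first exclusion criterion is "Supine systolic blood pressure (SBP) < 100 mmHg OR supine diastolic blood pressure (DBP) <60 mmHg".
- **Entry, section 11.3.3.** The paragraph on supine and orthostatic measurements says "Subjects with a supine systolic blood pressure >110 will be enrolled in the study". It gives no diastolic figure.
- **Before phase 2, section 4.3.3.** One of three findings at the phase 1 visit that do not stop a subject at once is "Supine systolic blood pressure < 90 mm Hg". Such a subject "will be scheduled for an ad hoc visit for reassessment of values prior to drug initiation in phase 2". The consequence is "If these criteria persist during the ad-hoc visit, the subject will be discontinued from the study". No diastolic limit is listed.
- **Crossover, section 5.5.** In phase 2 subjects take the drug they did not have in phase 1, "such that each subject will receive both study interventions in this cross-over design". Section 5.2 allocates the two sequences equally within blocks.
- **Risk, section 11.2.1.** Blood pressure is the first of the two main risks named for nitrate, and the section relies on exclusion criteria and blood pressure checks to control it.

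**The concern.** The phase 1 visit is the endpoint visit at the end of the first treatment phase, so the section 4.3.3 limit is the last numeric supine pressure rule before phase 2 drug. For a subject who had KCl first, phase 2 brings the first KNO3 dose. That subject may start KNO3 with a supine pressure that would have barred entry to the trial: a systolic value from 90 to below 100 mmHg, or a diastolic value below 60 mmHg.

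Two things are at stake. One is the safeguard against the risk that section 11.2.1 names first. The other is uniform conduct: with two entry figures and a third figure before phase 2, staff cannot tell from the text which limit applies, or whether the lower one was meant for subjects who have not yet had nitrate.

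**Working it through.** The plan states no figure on this point that could be reproduced. The check sets the limits side by side.

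| Point in the trial | Source | Systolic limit | Diastolic limit |
|---|---|---|---|
| Entry | 4.3.2 | excluded below 100 | excluded below 60 |
| Entry | 11.3.3 | enrolled above 110 | none given |
| Before phase 2 | 4.3.3 | recheck below 90; stopped if it persists | none given |

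**Conflict at entry.** A subject with a supine systolic pressure from 100 to 110 mmHg passes section 4.3.2 but does not meet the section 11.3.3 figure.

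**Gap between entry and phase 2.** Against section 4.3.2: 100 − 90 = 10 mmHg systolic. Against section 11.3.3: 110 − 90 = 20 mmHg systolic. The diastolic limit goes from 60 mmHg to none.

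**Subjects whose first KNO3 comes under the phase 2 rule.** With equal allocation, 22 / 2 = about 11. This counts subjects governed by the rule, not subjects in the gap.

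**Age of the entry reading.** Phase 1 lasts 4 ± 1 weeks (21 to 35 days) and washout 7 ± 3 days (4 to 10 days). The screening reading is therefore at least 21 + 4 = 25 to 35 + 10 = 45 days old when phase 2 starts, plus any time between screening and the first dose. Section 4.3.1 requires stable blood pressure medication only before entry. Section 5.8 discourages later changes but allows them.

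**State of the subject at the recheck.** Under section 5.4 no study drug is taken during washout, so a recheck before phase 2 is off drug, yet the 90 mmHg figure still applies. For a KCl-first subject neither the phase 1 reading nor the recheck follows any KNO3.

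**Other limits in section 4.3.3.** Among the ad hoc criteria, eGFR (below 30) and methemoglobin (above 5%) equal their entry limits. Serum potassium, a criterion for outright exclusion at the same visit, loosens from above 5.0 to above 5.5 mEq/L. The section therefore shows no single pattern.

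**Number of subjects in the gap.** The documents give no mean or standard deviation for supine pressure in this population, so this cannot be computed.

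**The case against.** The strongest reply is that these are two kinds of rule at two time points. Section 4.3.2 sets eligibility and section 4.3.3 sets continuation. A looser limit for continuing is common, potassium loosens as well, and under blinding the phase 1 reading is taken on KNO3 for about half the subjects. This stands as a plausible intention. It does not explain why the same figure governs an off-drug recheck, or why it covers subjects who have had no nitrate, and the text gives no reason.

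It is also fair to say that the entry limits apply to everyone at screening, before randomisation, and that the 90 mmHg rule applies to both sequences. A reader might infer that the safeguard itself depends on the randomised sequence. The documents do not support that. The sequences differ only in which rule stands nearest the first KNO3 dose.

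Other protections exist. Section 4.3.3 lets the investigator stop a subject for any condition that threatens safe completion. Orthostatic pressures are taken at the phase 1 visit. In phase 2 the dose rises only after a telephone call about symptoms at 1 week, and symptomatic orthostatic hypotension leads to exclusion. These lessen the concern, but none is a numeric supine limit.

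A reader might also take the fall in section 11.2.1 ("we found a mild (~12 mm Hg) asymptomatic reduction in blood pressure recorded at the time of our study visits") and conclude that a subject at the phase 2 limit would reach 90 − 12 = 78 mmHg. The documents do not support that as a prediction. The fall is not labelled systolic, it is described as asymptomatic, and ambulatory pressure did not fall. The same section cites a meta-analysis with about 4 mmHg systolic (90 − 4 = 86) and a single-dose HFpEF study with no change.

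**Conclusion.** The limits are inconsistent and should be reconciled. The two entry figures conflict outright. The lower limit before phase 2 differs from both without explanation and has no diastolic part. The systolic gap is 10 or 20 mmHg, depending on which entry figure is meant, and about 11 of 22 subjects start KNO3 with the looser rule as the nearest one. Only those who passed screening and whose pressure later fell into the gap are affected; that number is unknown and may be small or zero.

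This rests on two assumptions: that section 11.3.3 is meant as a requirement for entry, and that no operational document outside the protocol applies a further limit.

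A reader might infer that subjects in the gap are the most likely to be removed in phase 2, with loss of their KNO3 outcome. Nothing in the documents shows this, and stopping them before phase 2 would lose that outcome with certainty. A reader might also infer that the 90 mmHg figure is the wrong one. The documents do not show which figure is right. The case for a change is clarity and subject safety, not bias in the treatment comparison.

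**What to change.** Reconcile sections 4.3.2, 4.3.3 and 11.3.3 on supine systolic and diastolic limits, or keep the difference and state the reason. Either way, the text should say explicitly what applies to:

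- KCl-first subjects, who are nitrate-naive when phase 2 starts;
- the ad hoc recheck before phase 2 drug.

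The rule and its values are for the sponsor's clinicians to decide. Whatever they choose should apply to every subject, so that its use does not reveal the sequence.

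The cost is a change in protocol wording, possibly a few more ad hoc checks, and possibly an occasional subject who does not start phase 2.
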